5.2 Vulnerable Populations

It is important to document and mitigate the effects of incarceration on individuals and families, and thus we are focusing our intervention on previously incarcerated parents and their children. We are also interested in decreasing recidivism, which is a significant problem in the United States. Children with incarcerated parents are at risk for a host of problems and one of the hypothesized mechanisms is related to positive father involvement, improved parenting practices, and broader familial support.

The study seeks to enroll fathers previously incarcerated in jail or state/federal prison. This is a group of individuals who face significant barriers to being successful and engaged with their family after prison or jail, largely because of racially discriminatory practices used in society that results in disproportionate numbers of minorities incarcerated in prison and jail. Research to promote positive father involvement is needed to help improve fathers' own outcomes (e.g., reduced substance abuse and criminal activity), as well as the outcomes of their children (e.g., reduced stress, internalizing and externalizing behavioral problems).

We make sure that the reading level of all materials is at or below the 8th grade reading level. We read items out loud to all participants and pause to make sure that they understand the material. We have an NIH Certificate of Confidentiality to protect participant responses to sensitive questions and to questions that might elicit information about illegal behavior that should remain confidential. We remind participants that they can skip any items that they do not wish to answer. We conduct extra training with research staff so that they understand the importance of confidentiality and sensitivity to vulnerable populations.

While compensation will be provided, the amount of compensation we believe is not high enough to be considered overly attractive by participants as to take unwarranted risks or to affect the voluntariness of consent. We will also inform all study participants during the consent process that their participation will not in any way affect their parole or probation status, their sentence, or anything else related to their status as a formerly incarcerated individual.

For any participants that are on probation or parole, we will not notify their probation or parole agent of their participation - unless if the participant requests/requires that we do so - and would not share any information obtained in the study should we be asked. We have a Certificate of Confidentiality to ensure this safety mechanism can be fully implemented. In the event that a participant were to ask if we can inform their probation or parole agent of their participation in the study or if the probation or parole agent were to inquire as to their participation, we would simply provide that the individual is participating. We will abstain from providing any specific details of the participant or their time in the study beyond enrollment.

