3.0 STUDY OBJECTIVES AND ENDPOINTS

The aims of the pilot feasibility trial are to demonstrate:

- a) client acceptance of the treatment (e.g., retention)
- b) ability to recruit sufficient numbers of participants
- c) feasibility of delivery with the clients and therapists in the designated treatment settings

Specified measures will be collected at various times (e.g., client experience and satisfaction at post-intervention time points; outcome measures at pre- and post-intervention time points). Key outcome measures will assess father involvement, extended family relations, and child outcomes in addition to self-report criminal behavior, substance use, and recidivism for the fathers. Waves of data collection will occur: 1) prior to beginning the program, 2) immediately following the program, and 3) 3-months after completing the program. Data collection will be done with the father, caregiver, and child. This will be done virtually either by phone with research team members reading prompts to participants or by video conferencing where team members can virtually share screens and walk through documents together, or virtually with

research team members reading prompts and writing down answers. If not possible, it would take place in a private setting (ideally outdoors) where researchers and participants can be safely socially distanced.

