10.3 Risk/Benefit Analysis

Data will be stored securely according to campus policy; when necessary, identifiable or sensitive information will be stored separately from other study data and participant identities will be masked in publication and any other dissemination of study results.

Participants will be informed about all aspects of the study during consent and have the option to skip or withdraw from any activities that make them upset or uncomfortable, including skipping any questions in surveys or measures.

Personal, sensitive, or identifiable information is necessary to answer the research question(s) but it will be stored separately from other study data.

If a participant reveals illegal behavior, it will either be removed from the research record. If the information is shared as part of an answer to the research question and is needed for the purposes of the study, the data will be protected by way of secure storage according to campus policy, as well as by a Certificate of Confidentiality that will be obtained after the PI receives IRB approval.

Participants will be informed of the approximate length of study activities during the consent process and will be offered the opportunity to take breaks during the study activities if needed.

Participants will be informed that although groups will be held virtually, sessions will never be video or audio recorded.

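### Section 5.2 makes disclosure to a probation or parole agent the participant's choice, then has staff confirm participation on the agent's inquiry alone

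*Combined protocol and SAP*

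**What the plan says.** The relevant text is one paragraph of Section 5.2 (Vulnerable Populations), covering any participant on probation or parole.

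- **Opening rule.** "we will not notify their probation or parole agent of their participation - unless if the participant requests/requires that we do so". The same sentence adds that the team "would not share any information obtained in the study should we be asked".
- **Stated support for that rule.** "We have a Certificate of Confidentiality to ensure this safety mechanism can be fully implemented".
- **Later rule.** Two events are joined by *or*: the participant asks the team to inform the agent, or the agent asks the team. The second reads "if the probation or parole agent were to inquire as to their participation, we would simply provide that the individual is participating".
- **Limit on what is given.** "We will abstain from providing any specific details of the participant or their time in the study beyond enrollment".

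Earlier in Section 5.2, participants are to be told at consent that "their participation will not in any way affect their parole or probation status". Section 10.2 lists a confidentiality breach among the known risks.

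**The concern.** The opening rule puts the decision in the participant's hands. The later rule takes it away in the situation where it matters most, when a supervising officer contacts the team. A staff member answering that call has two instructions in the same paragraph, and the more specific one says to confirm. The officer then learns that a named person is in the study, although that person made no request and Section 5.2 asks for no permission.

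What is at stake is a privacy protection for a group that the protocol itself treats as vulnerable. Enrollment is not an empty fact either. Under Section 7.1 it means that eligibility was verified and consent given, and Section 3.0 says that the study asks fathers about their own criminal behavior and substance use. The officer would learn none of the answers, but would learn that the man is in a study that asks.

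**Working it through.** No figure in the plan bears on this point, so the check is a comparison of the text.

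**Step 1. The four possible situations under each rule.**

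| Participant has asked? | Agent has inquired? | Opening rule | Later rule |
|---|---|---|---|
| Yes | No | Agent is told | Agent is told |
| Yes | Yes | Agent is told | Agent is told |
| No | No | Agent is not told | No trigger, so not told |
| No | Yes | Not told, or not covered if *notify* means only unprompted contact | Participation is confirmed |

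The rules agree in three situations. In the fourth, the opening rule either forbids disclosure or says nothing, and the later rule requires it.

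**Step 2. Does a narrow reading remove the problem?** Suppose *notify* means only contact that the team starts, and enrollment is not information obtained in the study. The sentences can then stand together as a graded policy: no unprompted contact, no study data released, enrollment confirmed if asked. The result in the fourth situation is the same. The agent learns of participation with no request from the participant and no permission required by the section. The narrow reading eases the conflict of wording and leaves the exposure in place.

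**Step 3. What can be disclosed?** The last sentence of the paragraph stops at enrollment. Survey answers, attendance and other details of the participant's time in the study are barred. The exposure is therefore to the fact of participation only.

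**Step 4. What is said after withdrawal?** Two parts of the protocol point different ways.

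- Section 7.1 defines enrolled by completed screening, verified eligibility and consent. None of these changes when a person stops attending, so on this basis the answer to a later inquiry would be the same.
- Section 5.2 has staff say that the person *is participating*, which is a current status. Section 6.2 makes active status depend on attending, or making up, every parenting class.

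The text does not say which status staff should report once someone has left. That is a gap in the instruction, not a provision for disclosing dropout.

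**Step 5. The Certificate of Confidentiality.** Section 5.2 says that it is held. Section 10.3 refers to "a Certificate of Confidentiality that will be obtained after the PI receives IRB approval". The two statements should be reconciled, because Section 5.2 relies on the Certificate for this safeguard. The present point does not depend on which is current.

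**The case against.** The strongest defense is that the paragraph describes a deliberate, limited policy. The team never contacts an agent unprompted, never releases study data, and confirms bare enrollment if asked. On that view there is no flat contradiction. Section 5.2 describes the Certificate as protecting responses to sensitive questions, and no responses are released. The consent pages are not available here, so participants may be told of confirmation on inquiry and may agree to it.

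Much of this stands. The sentences can be reconciled, the disclosure is narrow, and it cannot be said that participants are uninformed or have not agreed. What the defense does not reach is that Section 5.2, as the instruction to staff, attaches no permission to the agent's inquiry.

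Three stronger readings are tempting, and the documents do not support them.

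- *Supervision drives retention, so retention no longer shows client acceptance.* Section 3.0 does use retention as its example of acceptance. But nothing says that agents require, reward or monitor attendance, and details of time in the study are withheld from them. This is conjecture. It would not justify splitting the retention of about 15 fathers by supervision status in a descriptive pilot that tests no feasibility hypothesis (Section 9.1).
- *A repeat inquiry reveals dropout.* The limit to enrollment and the fixed definition in Section 7.1 count against this. The wording is unclear, no more.
- *The consent assurance is broken.* That assurance concerns consequences for parole or probation status, not secrecy. Confirming enrollment does not contradict it.

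**Conclusion.** The point holds as a confidentiality and wording fault in Section 5.2. Staff following the text would confirm a named person's participation to a supervising officer on the officer's inquiry alone, although the paragraph opens by making disclosure depend on the participant's request. The exposure is limited to enrollment status. What staff say after withdrawal is left open.

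No size can be given. The documents do not state how many of the planned 15 or so fathers, or of the caregivers, are on probation or parole, or how often an agent would inquire. The conclusion needs neither number, since a single inquiry about a single supervised participant brings the rule into play.

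It rests on Section 5.2 as written. If the consent form already obtains permission for confirmation on inquiry, the practical exposure is smaller, but Section 5.2 would still need to say so. Nothing here affects the sample size, the endpoints or the analysis. The change should be made, but it does not put the trial's design in question.

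**What to change.** Delete the part of the sentence that lets an agent's inquiry trigger confirmation, and put a single rule in its place. For example: *Participation is confirmed to a probation or parole agent only if the participant has given written permission. Without it, staff neither confirm nor deny participation, whether the person is enrolled, has completed the study or has withdrawn.* Keep the existing limit, so that even with permission nothing beyond enrollment is given.

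To carry this out:

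- add an optional permission line to the consent form, so that participants who want or need their agent told can choose this at the start;
- give staff a short script for calls from agents;
- in the same edit, make Sections 5.2 and 10.3 agree on whether the Certificate of Confidentiality is in hand.

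The cost is part of one sentence replaced, one optional consent line and a script. The downside is an occasional extra step for a father who wants his agent told and did not give permission at consent. No new data items or analyses are needed.

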5.3 Subject Recruitment

The first tier of recruitment will be with fathers. Our first avenue for recruitment will be reaching out to participants from previous focus groups conducted with a congruent sample, as previously approved by the University of Wisconsin-Madison ED/SBS IRB (Study #: 2019-0409, PI: [name]). Participants in these focus groups filled out future contact forms which the study team will use to invite them to the community intervention. This recruitment will take place through phone calls, text messages, or email communications.

Second, we will advertise with a flyer that is posted in places that individuals in the study might frequent (e.g., social service settings, clinics, community centers, libraries). Similarly, the study team will be creating a Facebook page to post flyers on. As per the IRB guidance (<https://kb.wisc.edu/sbsedirbs/page.php?id=42376>) simply posting recruitment materials through online platforms is generally not considered "Use of New Media" and since it will not be a means of data collection no privacy statement, terms of use, or consent is required. Again, these mechanisms of recruitment will not require any face-to-face communications and thus will fit any socially distanced guidelines that public health officials may have in place. In addition, we will host a Facebook Live Event using an already approved group recruitment script. Prospective participants will have the option of providing their name and contact information in a UW-M Qualtrics survey that will be available only to the research team. This will ensure confidentiality instead of the person providing the information publicly.

A third avenue of recruitment will come from recruitment with partner agencies, such as JustDane referrals through their Journey Home, Phoenix groups, Renewal After Prison group, or service fair that is offered to individuals recently released from prison; The Beacon (day shelter for homeless populations) with their

array of services provided to vulnerable groups; Nehemiah's Man Up group for currently and previously incarcerated men; and the Urban League with their fatherhood and child support initiatives. We will post flyers at these agencies if allowed or send flyers via email, but also work with program staff there to identify and recruit potential participants if allowed. Through these processes, we will invite people to call or to meet virtually with the research team to get information about the community program and screen them for study participation upon initial contact. We will follow the lead of each individual community organization as to how they have been delivering services during the pandemic. For those holding groups virtually, we will inquire as to joining a session virtually, as well, to advertise and to tell interested/eligible individuals about our study and ask that they reach out to us via phone or email.

Anyone who contacts the study team via email will be provided with the study flyer and basic email text with study details.

Stated explicitly, through each of these approaches, interested participants will be invited to contact the study team (most likely via phone call, but also through email or text message via Google phone) for screening at a later time if not available to be screened on the spot at the time of original recruitment contact. During these contacts, research team members will provide more details and information regarding the community intervention and check inclusion criteria. As alluded to, group recruitment methods may also be used. For example, if a Phoenix group meeting is occurring at JustDane (previously Madison-area Urban Ministry) remotely, participants will be asked by staff ahead of time for their voluntary participation in a 10-minute group presentation in which one of the research team members will also join the group virtually to inform individuals of the study and possibly to participate if they are interested and meet the eligibility criteria. A project phone number will be given to participants to call to get more information. Flyers, group recruitment scripts, and phone scripts are all attached herein.

Once a study team member verifies that a father is eligible for participation and he agrees, he will provide the name and contact information of the primary or secondary caregiver (depending on the status they currently hold, themselves). The caregiver will be contacted if the child is cared for primarily by the caregiver and not the father. Individuals who are caring for the focal children of participating fathers are identified as caregivers. Based on previous research, we expect most of these caregivers to be either the other biological parent or a relative of the child.

The study team will then reach out to the caregiver to confirm interest in enrolling the child in the study through phone, text message, or email. If the caregiver does not respond or does not wish to have their child enrolled, we will notify the father that he may still enroll but that we will not be able to collect data from their child. We will place initial calls or send initial emails no more than 3 times to caregivers before ceasing communication. At that time, we will assume they are not interested in having their child participate, or themselves, and notify the father.

If a father has more than one qualifying child, one child will be randomly chosen for participation. We will not require that a child be the biological child of the participating father.

While staff at JustDane, the Beacon, Nehemiah, or the Urban League may help refer potential participants to the study, as would other service providers who have recruitment flyers at their locations, they will not actively recruit. If a potential participant were to inquire about the study or express interest, the staff at the respective agency would be instructed to refer the prospective participant to the study team for information.

All participation will be voluntary for the study respondents.

In addition to posting flyers at social service institutions, businesses, community centers, clinics, libraries, and churches with their permission, the research team will work directly with staff at community organizations (e.g., Just Dane) to share flyers and information about the study with individuals served at their agencies who might be eligible and interested. At no time, however, will staff at community agencies be asked to answer questions about the study or to explain study procedures. Instead, prospective

participants will be guided to contact the study team directly at the email address or phone number on the flyer.

6.0 BEHAVIORAL/SOCIAL INTERVENTION

6.1 Study Behavioral or Social Intervention Description

The Pathways for Parents after Incarceration Program (P4P) is an 8-week intervention that focuses on strengthening parenting skills, building constructive co-parenting strategies, providing therapeutic social support, and connecting families to needed specialized services. P4P is based on an adapted version of Parenting Inside Out (PIO), a cognitive behavioral parent management skills training program originally designed for parents in prison.

P4P is delivered remotely over Zoom (owing to the COVID-19 pandemic) but in real time. Participants first pick up materials needed for the intervention (e.g., intervention manual, laptop/tablet, office supplies, other materials), and then participate from home or other location of their choice. Eight didactic sessions (once per week for eight weeks) are completed along with eight therapeutic sessions (these run back-to-back). Trained PIO coaches deliver the didactic classroom portion and trained therapeutic clinicians deliver the therapeutic sessions. The PIO or classroom portion lasts 2-2.5 hours each, and the therapeutic session is 1 hour each week (total time = 3-3.5 hrs/week).

Staff who will administer the intervention must first complete a PIO training offered by the organization who owns the curriculum rights to the intervention, The Pathfinder Network (<https://www.thepathfindernetwork.org/>). Clinical staff who facilitate the therapeutic sessions must be trained and licensed clinicians in social work, counseling, psychology or related fields. Intervention fidelity will be monitored using the Parenting Inside Out Group Observation Feedback Form Score. Domains scoring in the low category (1=remediation is needed or 2=a growth area) will signal inadequate fidelity requiring re-training and further monitoring. This will be done through individual meetings with the interventionist and with written feedback.

6.2 Study Intervention Compliance

Adherence to the protocol will be assessed by documenting the number of participants recruited, consented and enrolled, and attendance of participants in weekly PIO and therapeutic sessions. Completion of study interviews (measures and qualitative interviews) will also be tracked. To remain an active participant in the study, participants must attend all PIO sessions and if any are missed, attend a makeup session with a coach. Attendance records are carefully monitored and tracked. Participants who drop out of the study once the sessions begin will not be replaced.

7.0 STUDY VISITS AND PROCEDURES

7.1 Screening and Enrollment

[The Screening and Enrollment visits and procedures are described in detail below.]

Informed Consent

Father respondents will participate in an oral consent process to take part in the screening process. Using an oral consent script, the researcher will describe the purpose of the study, the screening process and its purpose, what questions will be asked on the screening instrument, and that the information collected during the screening process will be retained for research purposes regardless of whether they enroll in the study. Participants will then be asked whether or not they wish to participate in the screener to see if they will be eligible to participate in the full study.

The potential participants who respond to community postings or to information materials that are provided by community partners will be instructed to email or call the study team. Contact details will be provided on information sheets and flyers. Potential participants who respond to the posted flyer or the

provided information will be asked to set up an over-the-phone time to complete the brief screening form and obtain contact information for the formal invitation and subsequent reminders for the intervention. If eligibility and exclusion criteria are met, they will be invited to participate in the full consenting process after the screening.

Researchers will determine if they are legally eligible to provide parental consent for their child. If so, participating fathers will take part in the consenting process for the eligible child. Children will participate in the consenting process after the father consents.

If the father is unable to legally provide parental consent for the child, researchers will determine if the caregiver is legally able to provide parental/legal guardian consent. If so, the caregivers will participate in the consenting process for the eligible child, children under the age of 5 will not provide assent, children 5-10 years old will participate in an oral assent process, and children aged 11-17 years old will participate in a written assent process. If neither the jailed parent nor the caregiver is legally able to give parental consent for the eligible child, based on the exclusion criteria the family will not be able to participate.

The consent process will take place virtually or in person (assuming COVID safe) prior to baseline data collection. If the father is legally able to provide consent for the child, the study team member will meet with the father and child virtually (by video call or phone) or in person, prior to the first session. The research team member will read each consent form out loud to the participant to which it pertains. Following that, the team will ask for written consent on the forms.

If the father is not the legal guardian and cannot consent for the child, the study team member will meet with the caregiver and child virtually or in person (similar to the procedure for fathers). The research team member will read each consent form out loud to the participant to which it pertains. Following that, the team will ask for written consent on the forms.

Participants will receive the forms either through mail, email, or delivery through a safe procedure in which there will be no contact during the consent drop off. Once signed, participants will be allowed to either scan, take a picture and send, or coordinate for a safe and secure pick up in which a research team member obtains the form with no contact (e.g., taking it from a mailbox). If consent is done in person, the signed consent form will be obtained at that time.

Fathers will sign a consent form that includes signed parental permission for the child. Children younger than 5 years old will not provide assent as we believe children ages 3-4 years old will not be able to understand the study. When developmentally appropriate, the researcher will describe the activity (asking interview questions) using language that is accessible to young children before engaging in the activity with the child. Children ages 5 to 10 years will be asked to provide verbal assent. Children ages 11-17 will be asked to provide written assent. When the father is not able to give consent for the child to participate, the caregiver will be asked to provide consent instead.

Screening Visit

Once a prospective participant indicates interest in learning more about the study, the researcher sets up an appointment over the phone or over video chat (e.g., Zoom) and screens the participant for eligibility using an established screener form. Once determined eligible, the participant is asked if they would like to continue and complete the consent process. This session lasts approximately 20-30 minutes.

Baseline

A baseline or pre-test survey is completed after the participant is deemed eligible and they complete the consent process. This is either done in the same session as the screener and consent or at another time. The baseline survey is estimated at 1.5 hours.

Enrollment

A research participant will be defined as “enrolled” in the study when they meet the following criteria:

- The subject and study staff have completed all screening documentation and the person is deemed eligible.
- The PI has verified that the subject meets all of the inclusion criteria.
- The PI has verified that subject meets none of the exclusion criteria.
- The subject has been consented by study staff.

